- VIII. Change in ± 0.75 DS/DC in the spectacle prescription [15-20].

Intervention

Participants in the intervention group will wear the newly designed SESL01 lens. The SESL01 is an Enhanced Single Vision Lens design. Enhanced Single Vision Lenses (ESL) have a small amount of positive power towards the bottom of the lens, as this is the area that is in line with the eye when looking downwards for near tasks. The small amount of positive power is expected to reduce the effort by the eyes to maintain a clear, in-focus image when looking at tasks at near.

Patients in the control group will be corrected with standard single vision lenses with an anti-reflection coating.

[figure not shown]
Both patient groups will have a choice of spectacle frames (within a set price range of up to £70) to select for their new spectacle correction. At the end of the study, all spectacles will be returned to the research team so that they can be reglazed with standard single vision lenses with an anti-reflection coating ensuring that the intervention lens (SESL01) is not in the public domain ahead of its official release.

Table 1 Schedule of enrolment, intervention, and assessments

	Study period					
	Enrolment Screening	Allocation Baseline	Spectacle collection	Post-allocation		Closeout
Timepoint (weeks)	-W0	W0	W2	W6	W10	W14
Enrolment						
Eligibility screen for patients	x					
Informed consent for patients		x				
Randomisation for patients		x				
Spectacles collection			x			
Intervention Group will use the Super Enhanced Single Vision Lens L01 (SESL01)			x	x	x	x
Control Group will use the standard single vision lenses			x	x	x	x
Assessments						
Computer Vision Syndrome Questionnaire (CVS-Q)	x	x		x	x	x
LogMAR Vision and Visual Acuity (using a computerised chart: 6/6 minimum monocular distance VA and N6 monocular)		x		x	x	x
Non-cycloplegic refractive error assessment (anisometropia of ≤ 1.50 DS in any one meridian, +4.00 to 6.00DS and +2.00DC)		x				
Cover test (D&N)		x				
Ocular Motility		x				
Pupil size (D&N)		x				
Fixation Disparity (D&N)		x				
Monocular and binocular amplitude of accommodation		x		x	x	x
Near point of convergence		x		x	x	x
Slit lamp Assessment (including measuring of tear break-up time, less than 11sec is an exclusion criteria)		x				
Indirect assessment of the fundus (Volk)		x				
Optical Coherence Tomography imaging		x				
Intra-Ocular Pressure measurements for those aged 40yrs and over		x				
Visual Fields		x				

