Covid safety protocols:

Participants will be required to wear a face covering throughout the examinations while in the eye clinic (unless they are exempt). Before the visit, participants will be asked to complete a COVID-19 Research Participant Pre-Visit Check Form, which will be used to prevent the spread of COVID-19 and to reduce the potential risk of exposure. If participants are displaying any COVID symptoms, their data collection appointment will be rescheduled by a week. If participants display any COVID-19 symptoms during, or after the visit, the PI should be informed, so that the necessary steps can be taken according to relevant government guidelines.

The clinicians in the study will be wearing personal protective equipment, and all equipment and room surfaces will be cleaned between participant visits.

Harm

We do not expect adverse events or other unintended effects. All information regarding the trial will be included in the clinicians' and patients' information sheets.

[figure not shown]
Spectacle dispensing and prescribing can cause 'non-tolerance'. Non-tolerance is when a participant is not satisfied with their spectacles, which may be due to the lack of clarity of vision or discomfort caused by the frames [20].

Cases of non-tolerance [15] can be split into:

- I. Dispensing: This is where the fitting of the frame or the dispensing measurements were not correct for the participant.
- II. Prescription: The participant is not able to adapt to the prescription or there was a data entry error, and the incorrect prescription was ordered.

Cases of non-tolerance are small; research shows that cases in general optometric practice range between 1% to 3% [16]. The implication of this data for our study is that approximately 7 participants may report dissatisfaction with their spectacles. A procedure to handle cases of non-tolerance is summarised in Figure 2.

Figure 2 Process for handling non-tolerance

Process for dealing with a case of spectacle non-tolerance.

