Should symptoms of non-tolerance remain after the retest for the prescription and re-dispense, the information will be reported to Carl Zeiss Vision International GmbH c/o Carl Zeiss Vision UK Ltd as an adverse effect within 3 working days. Carl Zeiss Vision International GmbH c/o Carl Zeiss Vision UK Ltd has an adverse effect reporting template that will be filled in and sent to the relevant department within the lens manufacturer. Carl Zeiss Vision International GmbH c/o Carl Zeiss Vision UK Ltd will inform MHRA about any adverse effects.

Auditing

No audit has been planned at this time.

Research and dissemination

The study protocol and outcomes will be published in peer-review journals, conference papers and may be used in training materials for clinicians working in the optical industry.

Participants will be offered a copy of the final study report submitted to Carl Zeiss Vision International GmbH c/o Carl Zeiss Vision UK Ltd.

Regulatory approvals

Ethics approval will be sought from and NHS REC, and from the UCLan University REC. A notice of no objection will be sought from the MHRA.

Protocol amendments

We are not expecting to make any changes to the eligibility criteria, outcomes, and analyses during our study. Any amendments made to the protocol will be submitted to the MHRA and/or REC as appropriate.

Consent, invitation, and confidentiality

Consent will be obtained according to the International Standards Organisation (ISO) 14155 – Clinical investigation of medical devices for human subjects – Good clinical practice guidelines. The Chief Investigator (CI) or other qualified member of the study team will make the decision as to whether the potential participant is suitable for screening and/or enrolment into the study. The potential participant will then be given the patient information leaflet and consent form and will have a discussion with the study team member.

The potential participant will then be given time to consider taking part and take the opportunity to discuss the study with others such as friends and family or members of their medical team, as applicable and appropriate. Once the potential participant is satisfied that they have been fully informed, and they have decided that they wish to enter the study, they will be asked by the study team member to sign a consent form.

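### Non-tolerance is reported as an adverse effect only if it persists after retest and re-dispense, so cases that settle are left out, and no count by arm is planned

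*Combined protocol and SAP*

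**What the plan says.** The Harm section defines non-tolerance by what the participant experiences, whatever the cause: "Non-tolerance is when a participant is not satisfied with their spectacles, which may be due to the lack of clarity of vision" or frame discomfort. It then describes two groups of cases. The first is dispensing: "This is where the fitting of the frame or the dispensing measurements were not correct for the participant". The second reads "Prescription: The participant is not able to adapt to the prescription or there was a data entry error". From a cited rate of 1% to 3% in routine optometry it concludes: "The implication of this data for our study is that approximately 7 participants may report dissatisfaction with their spectacles".

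The handling procedure is placed in Figure 2, which is missing from the text available for review. After the figure comes the reporting rule: "Should symptoms of non-tolerance remain after the retest for the prescription and re-dispense, the information will be reported to" the sponsor "as an adverse effect within 3 working days". The sponsor in turn "will inform MHRA about any adverse effects".

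Four other places bear on this:

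- **Intervention:** "At the end of the study, all spectacles will be returned to the research team so that they can be reglazed" with standard lenses. Ancillary post-trial care repeats this.
- **Table 1:** spectacles are collected at W2, assessments follow at W6, W10 and W14, and W14 is the closeout.
- **Aim and Outcomes:** safety stands beside effectiveness in the aim, and Outcomes says safety will be considered before wider prescribing.
- **Statistical methods:** there is no safety endpoint and no tabulation of non-tolerance or adverse effects by randomised arm.

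**The concern.** The quantity the protocol forecasts differs from the quantity it reports. The forecast covers anyone who says they are dissatisfied. The reporting rule covers only those still symptomatic after two corrective steps. A participant whose trouble goes away after those steps has had the anticipated harm, but under the stated rule has had no adverse effect.

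The lens design is what differs between the arms, and neither listed cause names it. A wearer who cannot get used to the added power low in the lens may be recorded as a prescription or fitting problem.

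At stake is the safety part of the aim. Non-tolerance is expected to be rare, no monitoring committee is formed and no audit is planned. If the reported adverse effects are the only safety output, the study could describe tolerability from a small and selected subset of cases, without comparing the arms.

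**Working it through.** **1. The protocol's own figure.** Inputs: 300 participants, 150 per arm (Randomisation); rate 1% to 3% (Harm). Expected cases = N × rate.

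- 300 × 0.01 = 3; 300 × 0.02 = 6; 300 × 0.03 = 9.
- The stated 7 corresponds to 7 / 300 = 2.3%, inside the range. The protocol does not say which rate it used.
- Per arm at equal rates: 150 × 0.01 = 1.5 to 150 × 0.03 = 4.5; for the figure of 7, 7 / 2 = 3.5.

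**2. What the rule would report.** Let s be the share of cases that settle after retest and re-dispense. Reported cases = 7 × (1 − s). The documents do not give s, so it is an assumption shown over a range.

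| s (assumed) | Reported of 7 |
|---|---|
| 25% | 7 × 0.75 = 5.25 |
| 50% | 7 × 0.50 = 3.5 |
| 75% | 7 × 0.25 = 1.75 |

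Over the whole forecast range, s = 50% gives 3 × 0.5 = 1.5 to 9 × 0.5 = 4.5 cases in both arms together.

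**3. Cases raised at closeout.** To meet the rule, a participant must report trouble, be retested, have spectacles re-dispensed, and still be symptomatic. Intervention has all spectacles returned at the end of the study and reglazed with standard lenses, and Table 1 puts the closeout at W14. A complaint first made at that visit leaves little or no time to wear re-dispensed study lenses. This is an inference: Table 1 has no row for the return, and no duration is given for retest or re-dispense.

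**4. Attribution.** The tested feature is positive power towards the lower part of the lens (Intervention). The dispensing cause covers fit and measurements. The prescription cause covers failure to adapt and ordering errors. A design-related case fits neither by name, though failure to adapt could absorb it.

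**5. How much information is lost.** This uses exact power of a two-sided Fisher test at 0.05 with 150 per arm. All rates are assumed, and in the last column half the cases in each arm settle and are not counted.

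| Control v SESL01 | All cases counted | Half settle, uncounted |
|---|---|---|
| 2% v 6% | about 0.30 | about 0.10 |
| 2% v 10% | about 0.80 | about 0.40 |

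The trial is weak on moderate differences even with full counting.

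**The case against.** The rule governs reporting to the sponsor. It does not say that earlier cases go unrecorded. Figure 2 holds the procedure and could include a log from first contact. Reasons for discontinuation are also documented, which gives a second, partial route, since participants may withdraw without giving a reason. This stands: a reader might infer that settled cases leave no trace at all, and the visible text does not support that. It shows only that they are not adverse effects under the stated rule.

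A reader might also infer that intolerance of the SESL01 design cannot be counted. The documents point the other way. The trigger is persistence, whatever the cause, and intolerance of the design is the kind that a corrected prescription or refit may fail to remove. Assumed rates show that the direction is open. Take 2% v 6%, which is 150 × 0.02 = 3 cases against 150 × 0.06 = 9. If two thirds settle in both arms, the reported counts are 1 v 3. If two thirds of 3 background cases settle in each arm but the 6 excess SESL01 cases persist, they are 1 v 1 + 6 = 7, a sharper contrast than 3 v 9. So the claim that the rule must hide a difference, or must remove most events, does not follow.

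Nor does the text force a cause code. It offers the two groups as a possible division, and Inclusion criteria give enhanced single vision lenses as an example of a near add, so failure to adapt to the added power could reasonably be put under prescription. In a blinded randomised trial an excess is attributed by comparing arms, so a clinician's code adds little.

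Finally, the rule sets no onset window. It would be wrong to say that late-arising cases are excluded as such, or to name a cut-off week. Only the practical difficulty at closeout remains.

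**Conclusion.** The point holds in a limited form. In the visible text, persistence after retest and re-dispense is the only stated route by which non-tolerance becomes an adverse effect. Settled cases fall outside it, and cases first raised at closeout are unlikely to meet it. Persisting design-related cases are reportable but may not be attributed to the design. With no count by arm planned, the safety aim has no stated analysis for the one harm anticipated.

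The size depends on a share the documents do not give: between about 1.75 and 5.25 of the forecast 7 cases would be reported if 75% down to 25% settle. This rests on the 7 applying to the trial population and on Figure 2 and the case report form not already providing a full log. The change is worth making because it alters a stated rule at very little cost.

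**What to change.** In the Harm section:

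- Record every non-tolerance case at first report, at any visit including W14, with date, action taken and outcome (settled, persisting, or unresolved at study end).
- Keep persistence after re-dispense as a severity marker instead of the condition for entering the count.
- Optionally add a cause for cases not explained by fitting or prescription, assigned while blinded.

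In Statistical methods, add a table of all cases and of persisting cases by randomised arm, with 95% confidence intervals. This is essential: fuller recording alone does not answer the safety question.

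If Figure 2 or the case report form already logs all cases, say so and build the table from that log. The change concerns recording and tabulation and leaves the handling of affected participants as it is.

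The cost is protocol and form wording, a few more reports, and a less favourable-looking count in both arms. With about 7 cases expected the comparison will be imprecise, and the report should say so.
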